Other theories on the mechanism of BFR on tissue healing involves the acute inflammatory response during blood flow restriction. IL-6 is a cytokine released after exercise in response to muscle microdamage, and plays a role in skeletal muscle regeneration by recruitment of inflammatory cells.³⁴ As with IGF-1, IL-6 also contributes to the activation and proliferation of satellite cells, as well as activating the mTORC-1 pathway.^{35, 36} It is important to note, however, that while the studies above have been performed in the setting of BFR use on healthy individuals, the mechanism of action in injured patients has not been evaluated. Furthermore, these studies have only measured blood markers prior to BFR cuff placement and immediately after, with none evaluating the trend in changes of markers over multiple sessions of BFR therapy.

Objectives

Aim 1: To determine whether patients with non-surgical rotator cuff and biceps tendinopathy undergoing BFR rehabilitation show increased improvements in shoulder function relative to patients undergoing routine therapy with a tourniquet that is not occluding arterial blood (i.e. sham BFR). We hypothesize that patients undergoing rehabilitation with BFR tourniquet pressurized to recommended therapeutic specifications will have increased muscle strength and CSA, as well as higher functional score averages compared to patients undergoing rehabilitation with sham BFR. We will be measuring shoulder strength in injured and non-injured arms for both study groups using a Biodex testing machine. Ultrasound will be used to measure the CSA of the rotator cuff muscles. Both strength testing and ultrasound measurements will be performed before and after the rehabilitation protocol has been completed. Patients will receive questionnaires evaluating shoulder function at baseline, once cleared by physical therapy, as well as 6 and 12 months after completing rehabilitation.

Aim 2: To determine whether trends in blood biomarker concentration differ between both groups throughout the rehabilitation protocol. We hypothesize that patients undergoing BFR will have higher

Protocol version:

Template updated 9.24.14

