trends in GH, IL-6, and IGF-1 over the 6 week rehabilitation protocol. Patients will receive the blood draws in clinic at the following time points: prior to 1st day of rehabilitation, half-way through the protocol (approximately 3 weeks), and after completing rehabilitation (approximately 6 weeks). ELISA will be used to quantify GH, IL-6, and IGF-1 plasma levels at the 6 time points. The trends in these 3 blood markers will be compared between the two groups.

Methods and Measures

Design

Describe the basic design of the study, use as many of the following terms as apply.

- *For intervention studies: randomized controlled trial; placebo-controlled; before-after trial; pilot study*

Setting

Academic medical center

Subjects selection criteria

• Inclusion Criteria

- Inclusion criteria will be any injured patient ages 18 to 55 years with clinical and magnetic resonance imaging (MRI) consistent with a formal diagnosis of non-operative rotator cuff and/or biceps tendinopathy, no prior upper extremity ipsilateral procedures or history of deep vein thrombosis, and those willing to be part of the study.

• Exclusion Criteria

- Exclusion criteria includes patients younger than 18 or older than 55 years of age, a history of revision surgery or prior ipsilateral upper extremity surgery, concomitant ligamentous, tendinous, or cartilage injury that would alter postoperative rehabilitation protocol, inability to comply with the proposed follow-up clinic visits, and patients lacking decisional capacity.

• Sample Size

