Isocentric shoulder strength will be measured for injured and non-injured arms for both groups at baseline, half-way through the strength training phase of rehabilitation, and once rehabilitation has completed. A biomed testing machine will be used to evaluate changes in strength over time. Shoulder strength measurements will include shoulder flexion, abduction, external rotation, and internal rotation, as well as elbow flexion. Strength testing will be performed prior to beginning the rehabilitation session. Each test will be performed 3 times and the measurement will be averaged.

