Ultrasound will be used to quantify the changes in rotator cuff muscle before and after therapy. As previously described, the supraspinatus and infraspinatus muscles will be measured in each patient using a standard technique.²⁷ A multifrequency linear transducer (5-15 MHz) on a GE Logic S7 Expert will be used throughout the study. In order to measure the supraspinatus, the patient will sit in a chair, with the examiner standing behind the patient. The muscle belly of the supraspinatus and infraspinatus muscles will be evaluated while the patient had their hand placed on the anterior ipsilateral thigh for the examination. The muscle bellies of the supraspinatus and infraspinatus will be measured in the perpendicular plane to the long axis of their central tendon and muscle bellies to measure their respective cross sectional area and circumference. Landmark for obtaining measurement of the supraspinatus will be obtained by palpating the posterior corner of the acromion and measuring 8 cm medially along the spine of the scapula. From this position the transducer will be placed in the plane perpendicular to the spine of the scapula to visualize the cross section of the supraspinatus muscle belly and its central tendon. Landmark for obtaining measurement of the infraspinatus will be obtained by palpating the posterior corner of the acromion and measuring 5 cm medially along the spine of the scapula. From this position the transducer will be placed in the plane perpendicular to the spine of the scapula to visualize the cross section of the infraspinatus muscle belly and central tendon. Because the footprint of the transducer is smaller than the width of the muscle belly, panoramic images acquisition will be accomplished using LOGICView mode. The panoramic glide will be stopped once the full myofascial border between the infraspinatus and teres minor were in view. The difference between pre- and post-therapy cross sectional area of each muscle will be compared between both BFR and sham BFR groups.

Blood Biomarkers

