Blood samples will be acquired at baseline prior to intervention and at specific time points throughout the rehabilitation process to evaluate the effect of BFR therapy on the recovery of muscle, tendon, and ligamentous damage. Samples will be collected prior to beginning physical therapy, half-way through the structured protocol, and once the patient has completed rehabilitation. These blood samples will be collected by a member of the research team, who is trained in phlebotomy and is someone other than the principal investigator, and stored in a locked freezer until all samples for all patients have been collected. The patients will receive the blood draws in the physical therapy clinic on the day of their rehabilitation appointment. Once completed, GH, IGF-1, and IL-6 will be quantified using ELISA assays performed in the Wake Forest orthopedic surgery department. Each sample will have 3 technical duplicates analyzed to avoid loss of data during sample processing.

Patient Functional Status

Protocol version:

Template updated 9.24.14

Shoulder/Elbow functional status will be assessed using the following questionnaires that have been previously vetted for evaluation after upper extremity surgery: *Quick Disabilities of the Arm, Shoulder, and Hand (DASH)* survey, American Shoulder and Elbow Surgeons (ASES) standardized assessment form, visual analog scale for pain and satisfaction, and return to sport/daily activity questionnaires.^{42, 43} Patient reported outcomes will be captured prospectively over the course of one year using the PatientIQ, a web-based data collection healthcare platform. A blinded de-identified email and/or text message will be sent at baseline, and once cleared by therapy, as well as 6 and 12 months after completing therapy. After three days, if a participant does not respond to the survey, a second email and/or text message will be sent. If the participant does not respond after three consecutive weeks, a phone call will be administered to encourage continued participation.⁴⁴

Outcome Measure(s)

- *Shoulder strength, and rotator cuff muscle cross sectional area,*
- *Blood markers: GH, IGF-1, and IL-6*
- *Patient reported outcome measures: DASH, ASES, visual analog scale for pain and satisfaction*

Analytical Plan

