There are potential risks in this study. Risks and side effects related to this study. Patients may experience discomfort, bruising and/or bleeding where the needle is inserted. Occasionally some people become dizzy lightheaded or feel faint. Infection may occur on rare occasions. Risks of blood flow restriction tourniquet includes development of a blood clot, which could result in breathing complications if the clot travels to the lung. These risks have been minimized by excluding patients with risk factors for blood clots, as well as ensuring that the cuff is inflated to standard measurements that limit this risk. Other risks for tourniquet use include pain and discomfort at the site. However, the standard protocol limits the compression of the tourniquet to 30 second intervals, and there are no reports of persistent pain after sessions. The benefit of BFR therapy in shoulder injury is unknown. It is possible that by being in the BFR rehabilitation group, rehabilitation process may be slower than undergoing rehabilitation with BFR included.

References

1. Steinberg L: *Baseball Has A Serious Injury Problem*. Available at: <https://www.forbes.com/sites/leighsteinberg/2018/07/24/baseball-the-most-dangerous-sport-in-america/>. Accessed November 2, 2018.
4. Mascarenhas R, Verma NN: Editorial Commentary: Muscle Atrophy After Arthroscopic Rotator Cuff Repair-Reversible? *Arthroscopy* 2016;32:2488-2489.

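### Final strength, ultrasound and blood measurements and the 6- and 12-month surveys are triggered by completing rehabilitation, so a patient who stops early has no scheduled final assessment

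*Combined protocol and SAP*

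**What the plan says.** The readable text makes completion of rehabilitation the trigger for each final measurement.

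- **Strength** (Shoulder Strength and Cross Sectional Area Measurement): measured "at baseline, half-way through the strength training phase of rehabilitation, and once rehabilitation has completed". Tests are done ahead of a rehabilitation session.
- **Strength and ultrasound** (Objectives, Aim 1): "Both strength testing and ultrasound measurements will be performed before and after the rehabilitation protocol has been completed". The ultrasound method itself is worded less strictly: "The difference between pre- and post-therapy cross sectional area of each muscle will be compared between both BFR and sham BFR groups".
- **Blood** (Blood Biomarkers): after baseline, samples are taken "half-way through the structured protocol, and once the patient has completed rehabilitation", and they are drawn "in the physical therapy clinic on the day of their rehabilitation appointment". Aim 2 adds an approximate date to the last draw: "after completing rehabilitation (approximately 6 weeks".
- **Surveys** (Patient Functional Status): sent at baseline, on clearance by therapy, "as well as 6 and 12 months after completing therapy". Aim 1 agrees.

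The BFR Protocol section gives the programme a nominal length of six weeks at two sessions a week. The Study Arms section says that Figure 1 shows the time points, but the figure is not visible in the text reviewed.

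The Analytical Plan names independent t-tests, chi-square tests and repeated measures ANOVA. It gives no analysis set and no missing-data method. The readable text has no early-termination visit and no rule for following a patient who stops therapy.

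**The concern.** An outcome visit that depends on finishing treatment is conditioned on something that happens after randomisation. Patients who stop drop out of the final comparison because of how the schedule is built, even if they would willingly attend. Randomisation protects the comparison of all patients assigned. It does not protect a comparison of those who finished, if the reasons for finishing differ between arms and are related to outcome.

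The documents leave room for such a difference. The BFR cuff is inflated to 50% of limb occlusion pressure, and the sham cuff only enough to stay in place. The risk paragraph, under Reporting of Unanticipated Problems, Adverse Events or Deviations, notes: "Other risks for tourniquet use include pain and discomfort at the site". With 8 to 12 patients per arm, one or two stoppers are a sizeable share of an arm. A final assessment that was never scheduled cannot be recovered at the analysis stage.

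**Working it through.** **Step 1. What a stopper would contribute under the written schedule.** Two sessions a week for six weeks is 12 sessions, so the midpoint falls at about session 6.

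| Measurement | Stops before the midpoint | Stops after the midpoint | Completes |
|---|---|---|---|
| Strength | baseline only | baseline, half-way | baseline, half-way, final |
| Ultrasound | baseline only | baseline only | baseline, final |
| Blood | baseline only | baseline, half-way | baseline, half-way, final |
| 6- and 12-month surveys | no start date | no start date | scheduled |

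A t-test on final values, or on change to final, uses completers only. Classical repeated measures ANOVA needs a complete row, so it would also discard the half-way blood value of a later stopper.

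**Step 2. The plan's own figure.** The plan gives no stopping rate and no dropout allowance, so there is no attrition figure to reproduce. Its one calculated figure, 6 per group for 90% power at a growth hormone effect size of 2.203, does reproduce. A two-sided 5% t-test (alpha assumed; the plan states none) needs 5.49, rounded up to 6, with power 92.9%. That figure is not in dispute here.

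**Step 3. Shift in an arm's mean.** Let m be the share of the arm that stops and g the difference, in SD, between completers' and stoppers' mean outcomes.

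Mean of all assigned = (1 − m) × completers + m × stoppers

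Completer mean − mean of all assigned = m × g

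Both the number of stoppers and g are assumptions. The arm sizes, 8 (minimum) and 12 (hoped for), come from Sample Size.

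| Stoppers in one arm | m | g = 0.5 | g = 1.0 | g = 1.5 |
|---|---|---|---|---|
| 1 of 8 | 0.125 | 0.06 | 0.13 | 0.19 |
| 2 of 8 | 0.250 | 0.13 | 0.25 | 0.38 |
| 2 of 12 | 0.167 | 0.08 | 0.17 | 0.25 |

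The between-arm difference shifts by (m × g in BFR) − (m × g in sham). It is zero if both arms lose patients equally and for similar reasons. Its sign depends on which arm loses patients and on whether they are poor or good responders.

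**Step 4. Scale.** The standard error of the difference is √(2/8) = 0.50 SD at 8 per arm and √(2/12) = 0.41 SD at 12 per arm. The illustrated shifts are therefore below one standard error.

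**Step 5. An extreme case.** In simulated trials with no true effect and normal outcomes, the two poorest responders were removed from the BFR arm only, and a two-sided 5% t-test was applied. At 8 per arm the bias was 0.38 SD and the type I error 12.1%. At 12 per arm they were 0.28 SD and 11.2%. This is a worst case for two losses, not an expectation.

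**Step 6. Precision.** Lost numbers matter less than bias. The effect detectable with 80% power moves from 1.51 SD (8 v 8) to 1.65 SD (6 v 8), and from 1.20 SD (12 v 12) to 1.26 SD (10 v 12).

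**The case against.** Several points against the concern have force.

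- **Figure 1 may hold a calendar schedule.** This cannot be excluded, so the point is limited to the readable text. If the figure does give fixed weeks, the text that ties measurements to completion would still need to be aligned with it.
- **Completion can be read as the end of a six-week programme.** The nominal length and the approximate date for the last blood draw support that reading. But the date qualifies completion rather than replacing it, applies only to blood, and does not say that a patient who has stopped is brought back.
- **Slow attenders are hypothetical.** No section says that missed sessions are made up before final testing. Late finishing would bias the comparison only if it differed by arm.
- **Retention steps exist.** Surveys are remote, with reminders and a telephone call. These address non-response to a survey that has been sent; they do not set a date for a patient who never completes. The exclusion of people unable to attend follow-up applies at entry.
- **Arm-related stopping is not documented.** The risk paragraph also says that lasting pain after sessions has not been reported, and sham patients wear a cuff too.

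A reader might infer that the plan specifies a completers-only analysis, or that the results would flatter BFR. The documents support neither. No analysis set is named, and half-way strength and blood values would exist for later stoppers. Sham patients might stop for lack of benefit, and patients in either arm might stop because they have recovered, so the direction of any bias is unknown.

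**Conclusion.** The concern holds in a limited form. Applied as written, the readable schedule gives a patient who stops early no final strength, ultrasound or blood measurement and no date for the later surveys. With the analyses named and no follow-up of stoppers, the final comparison would in practice rest on completers. This follows from the schedule itself and is more than an omitted detail.

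Whether bias results depends on stopping that has not been observed. The shifts of 0.13 to 0.38 SD (2 of 8) and 0.08 to 0.25 SD (2 of 12) illustrate its possible size. They assume two stoppers in one arm, none in the other, and a 0.5 to 1.5 SD difference from completers; they do not estimate what will happen. For a pilot of this size this is a change that should be made, because it is cheap and uses assessments already planned. It does not invalidate the design.

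**What to change.** Amend Objectives (Aims 1 and 2), Shoulder Strength and Cross Sectional Area Measurement, Blood Biomarkers and Patient Functional Status, and check Figure 1 against them:

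1. Schedule final strength, ultrasound and blood at the nominal 6 weeks from the first session, with a window (for example within 1 week), for every randomised patient whether or not therapy continues.
2. Send the later surveys at fixed months from the first session. Counting 6 and 12 months from the week-6 date would keep the intended spacing.
3. State that a patient who stops is still invited to the week-6 visit, including when there is no therapy appointment that day, and stays on the survey schedule.
4. In the Analytical Plan, analyse every patient in the assigned arm and state how missing values are handled. For example, a mixed model could use the half-way values.
5. Report sessions attended and stopping, with reasons, by arm.

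The cost is protocol wording, scheduling and a few recall visits; no new assessment is needed. Some slow attenders would be measured before their last session, so the comparison answers the effect of assignment rather than of the finished programme. An invitation does not guarantee that a stopper returns, so some data may still be missing. The change concerns the timing of measurement only, not treatment.

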Patients assigned to the BFR group will undergo BFR therapy during each session throughout the entire rehabilitation protocol. The standard rehabilitation protocol recommended by the physical therapists at WFBH is 2 sessions a week for 6 weeks. The therapy will be performed by one of the WFBH physical therapists who is trained and certified in using BFR therapy. The standard BFR protocol that is implemented by the Wake Forest physical therapists and recommended by expert opinion involve performing 4 separate exercises during each session. Each exercise will be done 4 consecutive times, starting with 30 repetitions, followed by 15 repetitions performed 3 times. Each set will be separated by 30 seconds break. After the finishing the 4 sets for one specific exercise, the patient will rest for 2 minutes prior to beginning the next 4 sets. In summary, the patient will perform 4 sets of 4 different exercises, perming the following repetitions: 30-15-15-15.

In the BFR group, the tourniquet will be pressurized to 50% limb occlusion pressure (LOP), which is the pressure necessary for occluding 50% of arterial limb flow in the upper extremity. The amount of cuff inflation is personalized to each patient as a safety measure and for maximizing the acute physiological response.⁴⁰ In the sham BFR group, the tourniquet will be pressurized to 0% occlusion pressure, while maintaining enough pressure to keep the tourniquet in place.

Protocol version:

Template updated 9.24.14

The tourniquet system (Delfi, Medial Innovations Inc) used in our physical rehabilitation clinic allows a patient specific LOP to be measured and automatically calculates the patient's personalized tourniquet pressure (PTP) as percentage of LOP. As an additional safety measure, the cuff automatically shuts off after 8 minutes to prevent prolonged restriction, and is locked from turning back on for 2 minutes. The sets for each exercise are structured so that the patient is able to finish 4 sets of one specific exercise within the 8 minute time limit.

Shoulder Strength and Cross Sectional Area Measurement

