Subject descriptive statistics will be analyzed using mean \pm standard deviation for continuous variables, and frequencies and percentages for categorical variables. Normality analyses will be performed utilizing data visual inspection and parametric testing. Averages between the two groups will be compared using independent T-test and chi-square analysis were appropriate. Repeated measures ANOVA will be performed to evaluate statistical significance in blood biomarkers.

Human Subjects Protection

Subject Recruitment Methods

Describe how and where subjects will be identified and recruited. Indicate who will do the recruiting, and tell how subjects will be contacted. Describe efforts to ensure equal access to participation among women and minorities. Describe how you will protect the privacy of potential subjects during recruitment.

- For studies using recruitment flyers and advertisements, please provide copies of these materials for IRB review.
- For studies using PHI to identify subjects via medical records search or referral from a treating physician, who will then be contacted, you will need a limited waiver of HIPAA authorization, If this applies to your study, please provide the following information:
 - Under this limited waiver, you are allowed to access and use only the minimum amount of PHI necessary to review eligibility criteria and contact potential subjects. What information are you planning to collect for this purpose?
 - How will confidentiality/privacy be protected prior to ascertaining desire to participate?
 - When and how will you destroy the contact information if an individual declines participation?

Protocol version:

Template updated 9.24.14

Informed Consent

Signed informed consent will be obtained from each subject. Informed consent will be gathered by the one of the study coordinators or study investigators in clinic after being screened with inclusion/exclusion criteria and prior to undergoing non-surgical treatment for the injury.

Confidentiality and Privacy

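### The strength-testing schedule differs between Aim 1 and the methods (two tests or three), and no analysis or contrast is specified for the half-way value

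*Combined protocol and SAP*

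**What the plan says.** The Objectives section, under Aim 1, gives two strength assessments: "Both strength testing and ultrasound measurements will be performed before and after the rehabilitation protocol has been completed". The section on shoulder strength and cross-sectional area gives three: one at baseline, one "half-way through the strength training phase of rehabilitation" and one at the end of rehabilitation. It covers five movements in both arms, each measured three times and averaged, and states that changes in strength over time are to be evaluated.

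The BFR Protocol section describes one programme: "The standard rehabilitation protocol recommended by the physical therapists at WFBH is 2 sessions a week for 6 weeks". BFR is used at every session ("Patients assigned to the BFR group will undergo BFR therapy during each session throughout the entire rehabilitation protocol"), and each session has the same content ("the patient will perform 4 sets of 4 different exercises"). It names no phases. For the blood draws, Aim 2 dates the middle sample as "half-way through the protocol (approximately 3 weeks").

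The Study Arms section foresees biomechanical assessment during therapy and refers to Figure 1 for all time points. That figure is not shown in this copy.

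The Analytical Plan compares group averages by independent t-test or chi-square, without naming an outcome or visit. Its only longitudinal method is for other data: "Repeated measures ANOVA will be performed to evaluate statistical significance in blood biomarkers".

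**The concern.** Shoulder strength is part of the Aim 1 hypothesis and comes first in the list of outcome measures, yet the text gives two schedules for it. The extra test is anchored to a phase mentioned nowhere else, so from the visible text it need not fall on the same day as the half-way blood draw.

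The analysis gap matters more than the wording. For muscle cross-sectional area, the measurement section at least names the pre-to-post difference as the comparison between groups. Strength has no such sentence. With three values per movement and a generic two-sample t-test, an analyst can test the final value, the half-way value or either change from baseline, and can choose after seeing the data. The t-test also cannot use a patient who has baseline and half-way values but no final one, which matters with 8 to 12 patients per arm.

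**Working it through.** **1. The plan's own figure.** The Sample Size section gives 6 per group for 90% power at an effect size of 2.203. With a two-sample t-test at two-sided alpha 0.05 (assumed; the plan states no alpha), power is 0.861 at n = 5 and 0.929 at n = 6, so 6 is reproduced. It rests on growth hormone, not strength, and does not change with this point.

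**2. The sections side by side.**

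| Item | Count |
|---|---|
| Strength tests in Aim 1 | 2 |
| Strength tests in the measurement section | 3 |
| Phases defined in the BFR Protocol section | 0 |
| Analyses naming strength in the Analytical Plan | 0 |

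**3. What the half-way test involves.** 5 movements x 2 arms = 10 averaged test values per patient, from 10 x 3 = 30 repetitions. For 16 to 24 patients that is 160 to 240 values (480 to 720 repetitions).

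**4. Error rate if half-way t-tests are added.** Injured-arm comparisons go from 5 to 10. If the tests were independent, the chance of at least one p < 0.05 under no effect would go from 1 - 0.95^5 = 22.6% to 1 - 0.95^10 = 40.1%. Strength measures are correlated, so these figures are too high. The documents give no correlations; the values below are assumptions. Null simulation, 8 per arm, 20,000 trials per row, two-sided t-tests on the value at each visit. The correlation between different movements at different visits is the product of the first two columns, except in the last row, where it is 0.2:

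| Between movements | Between visits | Any p < 0.05, final visit only | Any p < 0.05, either visit |
|---|---|---|---|
| 0.5 | 0.6 | 18.7% | 31.0% |
| 0.5 | 0.8 | 18.8% | 28.2% |
| 0.7 | 0.6 | 15.4% | 25.6% |
| 0.7 | 0.8 | 15.3% | 23.2% |
| 0.5 | 0.6 (cross 0.2) | 19.3% | 32.2% |

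This gives about 15-19% rising to 23-32%. Results at 12 per arm are nearly the same (15-19% and 22-31%).

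**5. What the half-way value adds for a patient without a final test.** Such a patient still has a baseline value, so the relevant quantity is the squared partial correlation of half-way with final, given baseline.
- Equal correlations r: [r/(1 + r)]^2. At r = 0.6, 0.375^2 = 14%; at r = 0.8, 0.444^2 = 20%.
- AR(1) with adjacent correlation r: r^2/(1 + r^2). At r = 0.6, 0.36/1.36 = 26%; at r = 0.8, 0.64/1.64 = 39%.

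**6. Longitudinal model against the t-test.** Take 8 per arm, one final test missing per arm, known covariance, unit variance and the same r of 0.6 to 0.8. The t-test on final values has variance 2/7 = 0.286. A three-visit model without baseline adjustment has 0.260 to 0.273, which is 4-9% lower. With complete data there is no gain unless baseline is adjusted for. In a model with a common baseline mean, leaving out the half-way value raises the variance by only 2-5%.

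**The case against.** Several points on the other side stand. Because every session is resistance exercise, the phase can be read as the whole 6-week programme, which puts half-way at about week 3, alongside the blood draw. Figure 1 may say so. The Study Arms section foresees assessment during therapy and the measurement section gives it a purpose, so the three-test schedule is not an isolated slip. Aim 1 points to baseline against end, and both schedules contain those tests. The protocol calls itself a pilot, no passage plans half-way t-tests, and the 15-19% at a single visit is general multiplicity that this conflict does not cause.

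These points limit the concern but do not remove it. Figure 1 could show which schedule is meant, but the two sections would still disagree and the Analytical Plan would still have no strength analysis. The plan does intend significance testing, so the tested contrast should be fixed beforehand, pilot or not.

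Three stronger readings are tempting and not supported:
- A reader might infer that the intervention has no strength-training phase. The text shows only that none is defined.
- A reader might infer that the half-way test serves no purpose. A purpose is stated; what is absent is an analysis.
- A reader might infer that the half-way value recovers the squared between-visit correlation, 36-64% at 0.6-0.8, of the information lost with a missing final test. That ignores the baseline value; given baseline, the figure is 14-39%.

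**Conclusion.** The point holds as an inconsistency in the schedule together with an unspecified analysis. Aim 1 and the measurement section disagree on the number of strength tests, the visible text does not define the anchor of the extra one, and no analysis or contrast is specified for strength over time.

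The effect on conclusions is modest: the baseline-to-end comparison survives under either schedule and the sample size is untouched. The rise in false-positive risk from about 15-19% to 23-32% is conditional. It requires half-way t-tests to be added and read on a par with the final ones, and it rests on assumed correlations of 0.5-0.7 between movements and 0.6-0.8 between visits. The 4-9% reduction in variance assumes one missing final test per arm at 8 per arm; the documents give no dropout rate. The change is still worth making because it costs little and closes the choice of contrast before data are seen.

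**What to change.** Make Aim 1, the strength measurement section and Figure 1 agree on the strength visits, and tie the half-way test to the same half-way point as the blood draw.

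In the Analytical Plan, analyse injured-arm strength, for each movement, with one longitudinal model over baseline, half-way and end of rehabilitation. Adjust for baseline or use a common baseline mean for the two arms, and apply a small-sample degrees-of-freedom correction. Name the arm difference at the end of rehabilitation as the tested contrast and the half-way difference as supportive.

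If the investigators do not want a longitudinal model, the minimum is one sentence calling half-way strength descriptive and naming the baseline-to-end comparison as the test, or removal of the half-way test. Either settles the contrast but does not keep patients who lack a final test in the analysis.

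The cost is wording in three sections and a check of Figure 1, with no new measurement. The downside of the model is slightly more analysis work and a covariance structure to be estimated from 8 to 12 patients per arm.
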